# **Improving Hallucinations by Targeting the rSTS with tES**

**NCT #: NCT05165654**

**June 13, 2025**

Protocol Number:	2019P001016X
Title:	Improving Hallucinations by Targeting the rSTS with tES
Design:	Double blind, sham controlled design with baseline, day 5 and 1 month follow up visits during which tES (cathodal tDCS or sham) was delivered to the right superior temporal sulcus (rSTS) from baseline to day 5 each day (5 days) twice a day for 20 mins. Participants were randomly assigned to either active cathodal tDCS or sham condition to test the effectiveness and feasibility of stimulating the rSTS using a novel targeting methodology consisting of a lesion network guided brain target linked to hallucinations.
Objectives:	Evaluate the effectiveness and safety of tDCS for improving the positive and general symptoms associated with individuals who have a history of hallucinations
Enrollment:	12 Individuals
Clinical Sites:	Beth Israel Deaconess Medical Center, Boston, MA
Patient Population:	Male or female outpatients 18-50 years of age patient's diagnosis with either schizophrenia, schizoaffective disorder, or psychotic bipolar as defined by DSM-5 or DSM-IV-TR criteria
Primary and Secondary Outcomes:	Primary Outcomes: Positive and Negative Syndrome Scale (PANSS); University of Miami Parkinson's Disease Hallucinations Questionnaire (UMPDH-Q); Auditory Hallucinations Rating Scale (AHRS). Secondary Outcomes: Global Assessment of Functioning (GAF); Young Mania Rating Scale (YMRS); Symptom Checklist 90 (SCL-90) Biological Motion; Steady State EEG (Visual, Auditory and Multimodal); Brief Assessment of Cognition (BAC); Montgomery-Asberg Depression Rating Scale (MADRS); Neurological Evaluation Scale (NES); Biological Motion.
Inclusion Criteria:	
 
1. Meet diagnostic criteria for schizophrenia, schizoaffective disorder, or psychotic bipolar disorder as verified by the Structured Clinical Interview for Diagnostic and Statistical Manual of Mental Disorders, 4th Edition, Text Revision (DSM-IV TR) and consensus clinical diagnosis
 
2. had no changes to relevant anti-psychotic medications for a period of 1 month prior to participation;
 
3. had a sufficient level of English to allow participation.
 
4. 18-50 years of age
 
 
In addition to the criteria above, participants for this stimulation procedure will be included if they have a history of hallucinations of any modality or experiencing moderate symptoms of hallucinations; and do not have a history of moderate-to-severe

	visual impairment secondary to glaucoma, cataract or macular degeneration.
Exclusion Criteria:	
 
1. metal implants in head.
 
2. implanted electronic devices.
 
3. history of neurological problems, seizure or head injury.
 
4. skin sensitivity.
 
5. claustrophobia.
 
6. organic brain syndrome
 
7. intellectual disability or other cognitive dysfunction that could interfere with capacity to engage in study as determined by the PI
 
8. a history of substance or alcohol abuse or dependence (other than nicotine) in the last 6 months or otherwise unable to commit to refraining from alcohol use during the acute period of study participation. The acute period of study participation is defined as during their visit and 24 hours before and after their visit.
 
9. Significant suicidal ideation or those who have enacted suicidal behaviors within 6 months prior to intake will be excluded from study participation and referred for appropriate clinical intervention.
 
10. Serious medical illness or instability requiring hospitalization within the last year.
 
11. Experience with any cardiac event.
 
12. Pregnant women, lactating women, women who are breastfeeding and women of childbearing potential who are not using medically accepted forms of contraception (e.g., IUD, oral contraceptives, barrier devices, condoms and foam, or implanted progesterone rods stabilized for at least 3 months).
 

Statistical Methodology:	Within and between comparisons to statistically detect differences in symptoms, visual/behavioral tasks and electrophysiology measures before and after treatment conditions (cathodal tDCS and sham). To determine the effectiveness and feasibility of targeting the rSTS with a novel targeting methodology to engage target outcomes.

**Statement:** The design, conduct and reporting of this trial shall be conducted in accordance with the protocol, the United States 45 Code of Federal Regulations (CFR) part 46 known as “The Common Rule”, 45 CFR 164.502(d), and 164.514(a)-(c) known as “The Privacy Rule” of the Health Insurance Portability and Accountability Act (HIPAA), and the International Conference on Harmonization (ICH)/Good Clinical Practice (GCP). All Investigators will have documented

training in The Collaborative Institutional Training Initiative (CITI Program) in Biomedical Research and GCP.

**Background:** Functional neuroimaging studies have identified neural correlates of hallucinations across multiple brain regions. Some studies suggest a common neuroanatomical substrate independent of the sensory modality, while others suggest different neural correlates for different types of hallucinations. However, whether these neuroimaging findings represented a cause, consequence or epiphenomenon of hallucinations was unclear until recently. Using lesion network mapping, researchers demonstrated that focal brain lesions play a causal role in the development of hallucinations and can occur in different brain locations, both inside and outside sensory pathway, and that greater than 90% of lesion locations causing hallucinations are negatively connected to the right superior temporal sulcus (rSTS). The rSTS is known to play a role in social cognition, biological motion, audiovisual integration, and speech. Hence, when spontaneous activity decreases at lesion locations causing hallucinations, spontaneous activity in the rSTS increases, the exact pattern thought to predispose to hallucinations. Additionally, functional connectivity within this region is abnormal in patients with visual and auditory hallucinations. Therefore, the association between rSTS connectivity and hallucinations would suggest this region may be optimal for modulation via non-invasive brain stimulation.

[figure not shown]
[figure not shown]
**Transcranial Electrical Stimulation (tES):** tES is a non-invasive brain stimulation technique which modulates cortical excitability by a weak electrical current [ $< 4$  milliamps (mA)] between two electrodes via direct current (DC), alternating current (AC), random noise (RN) or oscillatory current (OC). This study will utilize cathodal tDCS and a sham condition. Five days of twice a day (2x20min) of tES will be used during the week.

**Electroencephalography (EEG):** EEG is a routine, non-invasive procedure to record brain activity. EEG electrodes will be attached to the skin indirectly. Most of the electrodes are mounted in an elastic cap, which is fitted over the head and held in place with elastic straps. Some additional electrodes are placed next to the eyes, on the forehead, or behind the ears, and are held in place with adhesive collars. Electrical contact between the skin and the electrodes is achieved via a water-soluble electrode gel.

**Study Rationale:** Hallucinations are a core diagnostic feature of psychotic disorders. They involve different sensory modalities, including auditory, visual, olfactory, tactile, and gustatory hallucinations, among others. Hallucinations occur in multiple different neurological and psychiatric illnesses and can be refractory to existing treatments. Auditory hallucinations and visual hallucinations are found across diagnostic categories of psychotic disorders (schizophrenia, schizoaffective, bipolar disorder). Despite visual hallucinations being approximately half as frequent as auditory hallucinations, they almost always co-occur with auditory hallucinations, and are linked to a more severe psychopathological profile. Auditory and visual hallucinations at baseline also predict higher disability, risk of relapse and duration of psychosis after 1 and 2 years, especially when they occur in combination. Using a newly validated technique termed lesion network mapping, researchers demonstrated that focal brain

lesions connected to the right superior temporal sulcus (rSTS) play a causal role in the development of hallucinations. The rSTS receives convergent somatosensory, auditory, and visual inputs, and is regarded as a site for multimodal sensory integration. Here the investigators aim to answer the question whether noninvasive brain stimulation when optimally targeted to the rSTS can improve brain activity, sensory integration, and hallucinations.

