## **Study Visits and Details:**

Participants will complete baseline clinical, neuropsychological, visuoperceptual and neuro-physiological assessments (day 0), short-term follow-up (day 5) and long-term follow-up (month 1).

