## **OBJECTIVES**

### **Primary Objective**

The primary objective of this study is to evaluate the effectiveness of tDCS for improving the positive and general symptoms associated with individuals who have a history of hallucinations (PANSS, UMPDH-Q and AHRS).

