#### **University of Miami Parkinson's Disease Hallucinations Questionnaire (UMPDH-Q)**

Administer questions on severity of hallucinations (1-6) and questions of quality of hallucinations (7-20). Each hallucination type (e.g. visual, auditory, tactile, olfactory) experienced derives an individual score. Higher total scores mean worsening symptoms.

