### **Auditory Hallucinations Rating Scale (AHRS)**

A short 7-item clinician-rated scale measuring severity, frequency, duration, loudness, impact and distress level of auditory hallucinations presently experienced. Higher total scores mean worsening symptoms.

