## **Description of Study Endpoints**

### **Primary Endpoint**

Change from baseline to day 5 and 1 month in clinical measures (PANSS, UMPDHQ and AHRS) total score after 1 week of tES.

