### **General Statistical Considerations**

All collected study data will be collected on Redcap and processed using R and Matlab software. Descriptive statistics (n, mean, standard deviation, median, minimum and maximum) will be calculated by treatment group and sham group for continuous variables.

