### **Primary Analyses**

Primary Analysis of the primary, secondary, and additional efficacy endpoints:

Mixed Model Repeated Measures analysis (MMRM)/non- parametric methods will be used to compare using within group differences as well as to determine the difference between the two treatment groups on the primary, secondary and safety endpoints depending on the distribution of the data.

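### Does admitting people with only a past history of hallucinations undermine AHRS as a primary outcome?

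*Combined protocol and SAP*

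**What the plan says.** The Inclusion Criteria entry of the protocol synopsis takes participants for the stimulation procedure if "they have a history of hallucinations of any modality or experiencing moderate symptoms of hallucinations". The two conditions are alternatives, and neither is tied to the auditory modality. The Primary Objective describes the same population: "individuals who have a history of hallucinations (PANSS, UMPDH-Q and AHRS").

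The AHRS section says the scale covers, among other features, "impact and distress level of auditory hallucinations presently experienced". The Primary Endpoint is change from baseline to day 5 and 1 month in "clinical measures (PANSS, UMPDHQ and AHRS) total score". The UMPDH-Q section, by contrast, covers several modalities: "Each hallucination type (e.g. visual, auditory, tactile, olfactory) experienced derives an individual score".

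On analysis, General Statistical Considerations states: "Descriptive statistics (n, mean, standard deviation, median, minimum and maximum) will be calculated by treatment group and sham group for continuous variables". Primary Analyses uses MMRM or non-parametric methods to "determine the difference between the two treatment groups on the primary, secondary and safety endpoints depending on the distribution of the data". Neither section names a baseline AHRS threshold, covariate, stratum or subgroup.

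**The concern.** A participant whose hallucinations are all in the past, or were never auditory, can be enrolled with the lowest possible AHRS total. That score can only stay the same or rise. If a fraction *f* of participants is in this position and does not change, the between-arm difference in AHRS change is (1 − *f*) times the difference among those who could improve. A null AHRS result would then have two explanations: stimulation does nothing, or too few participants had anything to improve. An interval from all participants might also be read as ruling out a benefit that is present in people with current voices. The planned summaries would not give the number at the floor, so a reader could not judge which explanation applies. The apparent cure is cheap: baseline AHRS is already collected, so a supplementary analysis of those above the floor needs only SAP wording.

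**Working it through.** **Inputs.** From the documents: 12 participants, two randomised arms, AHRS change at two visits. Not in the documents: the allocation ratio, any AHRS effect or SD, the score that means no current voices, and *f*. There is no sample-size calculation to reproduce. Assumptions for illustration: 6 per arm, SD 1, a 1.0 SD effect in those above the floor, exactly zero change at the floor, two-sided 0.05, and 1 to 6 of 12 at the floor at random across arms. Worsening from the floor is not modelled.

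**Starting point.** With nobody at the floor, the noncentrality is 1.0 × √(6/2) = 1.73 on 10 degrees of freedom, which gives about 35% t-test power.

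**Dilution and its price.** The all-participant difference is 1.0 × (1 − *k*/12) for *k* at the floor. The other columns come from simulation with pooled t intervals (at least 200,000 trials per row).

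| At floor, of 12 | All-participant difference (SD) | All-participant interval wholly below 1.0 SD | Mean 95% half-width, all v above-floor (SD) | t-test power, all v above-floor |
|---|---|---|---|---|
| 1 | 0.92 | 3% | 1.23 v 1.33 | 31 v 31% |
| 2 | 0.83 | 5% | 1.20 v 1.43 | 27 v 28% |
| 3 | 0.75 | 7% | 1.16 v 1.55 | 23 v 25% |
| 4 | 0.67 | 10% | 1.11 v 1.70 | 20 v 22% |
| 6 | 0.50 | 21% | 0.99 v 2.20 | 12 v 14% |

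For *k* = 6, the above-floor half-width uses the 92% of trials with at least two per arm; for power, the remaining trials count as no rejection.

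**Which target?** The third column judges the interval against the effect in current auditory hallucinators. The nominal figure is 2.5%, and the above-floor subset keeps it. But the Primary Objective names people with a history. For them, with four at the floor, the true difference is 0.67 SD, and the all-participant interval lies wholly below that in 3.1% of trials. That is close to nominal. The 10% arises from changing the question, not from a biased analysis.

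**Does the subset answer the question?** To separate no effect from no room to improve, the subset interval would have to exclude either zero or 1.0 SD. With four at the floor it contains both in 76% of trials, against 71% for all participants. With nobody at the floor the figure is already 63%. With six at the floor it is 83% for the subset against about two-thirds for all. As an estimate of the above-floor effect itself, with four at the floor, the subset has a root-mean-square error of 0.73 SD. The all-participant difference has about 0.6 SD, despite its bias of 1.0 − 0.67 = 0.33 SD.

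**Rank tests.** The smallest exact two-sided p is 2/C(N, n). A 4 v 3 subset gives 2/35 = 0.057 and a 6 v 2 subset gives 2/28 = 0.071. With five or more at the floor, no subset can reach 0.05. With four at the floor, the chance of a 6 v 2 split is 2 × C(6,4)/C(12,4) = 30/495 = 6%.

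**What the planned tables show.** The baseline minimum by arm shows whether anyone is at the floor, once the scale's lowest score is known. With six in an arm, the median is the mean of the third and fourth values, so a median at the floor means at least four of the six are there. Exact counts are not given, but a severe problem would be visible.

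**The case for a change.** The best case for a change is that the Study Rationale asks whether stimulation can improve hallucinations, and a participant without any cannot answer that on AHRS. The Study Rationale also says that visual hallucinations nearly always accompany auditory ones. That makes never-auditory entrants unlikely but leaves the past-only route open. PANSS and UMPDH-Q do not rescue a null AHRS result, and the UMPDH-Q section gives no rating window, so that scale might share the limit. The all-participant interval also narrows as more people sit at the floor (1.23 SD with one, 0.99 SD with six) while centring on a smaller value, so it can look like firm evidence against an effect in symptomatic people. The data are already collected at day 0 ("Participants will complete baseline clinical, neuropsychological, visuoperceptual and neuro-physiological assessments (day 0"), so the cost is small.

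Most of this stands as a caution for interpretation. An AHRS null should not be carried over to people with current voices without knowing how many participants had them. What does not stand is the step to a prespecified subset analysis. It would add two AHRS contrasts (day 5 and 1 month) to three primary scales at two visits, with no multiplicity control named. It would also need special rules for small or empty arms, and its answer would be less decisive than the one it supplements. The synopsis describes stimulation in the past tense, so the analysis might be only post hoc in any case.

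**Conclusion.** The textual observation is right and the consequence is overstated. No stated rule or figure is wrong. Admitting people with a history is a deliberate choice, consistent between the synopsis and the Primary Objective, and the planned comparison estimates the effect in that population. Dilution relative to current auditory hallucinators could run from negligible (0.92 SD for a true 1.0 SD with one at the floor) to a halving (six at the floor), but nothing in the documents favours one figure over another. On the assumptions used, the subset analysis gains at most about two percentage points of t-test power, widens the interval at every floor count examined and, with four or six at the floor, is more often compatible with both zero and 1.0 SD.

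The remaining gap is one that analysts fill sensibly with 12 participants: give the number at the AHRS floor in each arm, show individual AHRS values at the three assessments, and discuss a null result with that count in view. Any above-floor summary should be descriptive, labelled post hoc if unblinded data have been seen, and not offered as settling the ambiguity. That is optional reporting, not a change to the plan.

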### **Secondary Objectives**

The secondary objective of the study is to evaluate the safety and tolerability of tDCS targeting the rSTS as well as secondary clinical outcomes including depression, mania, cognition, sensory integration, electrophysiology outcomes and global functioning

**Clinical and Cognitive Outcomes:** Symptom ratings will be collected using the PANSS, UMPDH-Q, AHRS, YMRS, MADRS, GAF, SCL-90 and cognition with the BAC

**Electrophysiology Outcomes:** A steady state evoked task will be implemented probing the auditory, visual and audiovisual integration capacity of mechanisms linked to the rSTS.

**Computerized behavioral tasks:** The biological motion task will be used to determine the effective targeting of the rSTS and prevention of off target stimulation. Lastly, to investigate the behavioral outcomes related to visual/audio perceptual functions, the NES will be employed to determine effective auditory and visual integration abilities.

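### The biological motion task cannot show that off-target stimulation was prevented, and an active-versus-sham difference cannot be credited to the lesion-network target

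*Combined protocol and SAP*

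**What the plan says.** The Design row of the synopsis gives targeting as a purpose of the randomisation: "Participants were randomly assigned to either active cathodal tDCS or sham condition to test the effectiveness and feasibility of stimulating the rSTS", and continues "using a novel targeting methodology consisting of a lesion network guided brain target linked to hallucinations". The Statistical Methodology row repeats the aim: "To determine the effectiveness and feasibility of targeting the rSTS with a novel targeting methodology to engage target outcomes".

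Secondary Objectives, under the computerised behavioural tasks, goes furthest: "The biological motion task will be used to determine the effective targeting of the rSTS and prevention of off target stimulation".

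The Background says what that task measures: "The rSTS is known to play a role in social cognition, biological motion, audiovisual integration, and speech".

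On the comparator, the section on transcranial electrical stimulation says "This study will utilize cathodal tDCS and a sham condition". The Primary Analyses section plans within-group comparisons and a comparison between the two groups, and nothing else. The Primary Objective is narrower than the synopsis: it asks whether tDCS improves symptoms and says nothing about site specificity.

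**The concern.** Two different questions are mixed. One is whether stimulation with this montage does better than sham. The other is whether any benefit arises because the current reached the rSTS and left other regions alone. The design randomises for the first question only. The sentence on biological motion nevertheless promises an answer to the second, from a task tied to the target itself.

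What is at stake is interpretation. If the plan is followed as written, a change on biological motion could be read as proof that stimulation was confined to the target, and a symptom difference from sham as support for the lesion-network method of choosing the target. Neither inference would have a comparison behind it.

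**Working it through.** The point turns on design logic, and no figure in the plan bears on it. The plan states 12 participants without alpha, power, effect size, SD or allocation ratio, so there is no calculation to reproduce.

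**Step 1: what biological motion can distinguish.** Take the plan's own premise that the task reflects rSTS function. There are four possible states of the world:

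| rSTS affected | Other regions affected | Expected on biological motion |
|---|---|---|
| yes | no | change |
| yes | yes | change |
| no | yes | no change |
| no | no | no change |

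The first two rows give the same result, and so do the last two. The task can separate rows 1 and 2 from rows 3 and 4, which is target engagement. It cannot separate row 1 from row 2, or row 3 from row 4, which is what sparing of other regions requires. This is the favourable case. The Background says the rSTS has a role in biological motion, not that it is the only region involved, so even the engagement reading is suggestive only.

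**Step 2: whether another outcome fills the gap.** The steady-state EEG measures probe auditory, visual and audiovisual processing linked to the rSTS, and the NES is used for auditory and visual integration. By the plan's account these also sit on the target side. The cognition, mood, mania, functioning and SCL-90 measures are secondary outcomes. None is named as a measure that should stay unchanged. Biological motion itself is a secondary outcome in the synopsis but is missing from the Secondary Endpoints section, and it has no success criterion. Adding it there would tidy the list but would not supply the missing information.

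**Step 3: what the randomised contrast identifies.** As a simplified additive sketch:

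active − sham = (effect through the rSTS) + (effect through neighbouring cortex) + (effect of current in general)

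There is one contrast and three unknown terms, so only their sum is estimated. Separating the first term would need a further contrast, such as the same current at another site. The number of participants assigned to such a condition is 0 of 12.

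**Step 4: whether a third arm is realistic at this size.** These are assumptions, since the plan gives none: two-sided alpha 0.05, 80% power, equal allocation. By the normal approximation, detectable difference = (1.96 + 0.84) × √(2/n per arm):

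- two arms, 6 each: 2.80 × √(2/6) = 1.62 SD (about 1.8 SD with the t distribution)
- three arms, 4 each: 2.80 × √(2/4) = 1.98 SD (about 2.4 SD with the t distribution)

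A control-site arm within 12 participants would weaken every pairwise comparison, so it would need a larger, justified sample.

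**The case against.** The strongest reply is that the trial does not need a control site for what it mainly asks. The Primary Objective concerns the effect of tDCS on symptoms, and sham is the right comparator for that. Feasibility needs no off-target arm either. No endpoint, estimand or success rule for site specificity exists, so there is no formal test to misreport. At 12 participants an extra arm would be impractical. All of this stands. It limits the point to the wording of the aims and to interpretation, and it does not rescue the sentence on off-target stimulation.

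Four stronger readings are tempting but lack support:

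- A reader might infer that the plan claims to test its targeting method against other methods. No section says so. The aim is effectiveness and feasibility of stimulating a target chosen in this way.
- A reader might infer that sham control makes the trial invalid. It does not, for the reasons above.
- A reader might infer from the montage listing (T8 at -1.5, three other electrodes at 0.5 each, and 3 × 0.5 = 1.5) that as much current goes off target as on. Return current has to balance in any closed circuit, and scalp electrodes are not brain regions. The documents as available give no field distribution, and figures are not shown. The sum says nothing about focality.
- A reader might infer that an existing measure, such as the BAC motor task, could serve as the off-target control. It belongs to a battery whose scores are a secondary endpoint, it adds no comparator, and no change on it in 12 participants would not show sparing.

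**Conclusion.** The statement that biological motion will determine prevention of off-target stimulation is wrong as written. On the plan's own description, the task is an on-target marker and can at most suggest engagement. The effectiveness-of-targeting wording in the synopsis needs a limit: a difference from sham would support this montage over sham, not the lesion-network target as its cause.

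The size is categorical. Site specificity has no randomised information behind it: 0 of 12 participants at a control site and no designated off-target outcome. This rests on reading the plan as a two-condition trial, which the Design row, the stimulation section and the Primary Analyses section all support. A field model in a figure that is not shown could inform expectation but would not replace a control condition. The sham comparison for the primary objective and the feasibility aim are unaffected.

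**What to change.** 1. **Secondary Objectives, computerised behavioural tasks:** delete the claim about off-target stimulation, and describe biological motion as an exploratory marker of target engagement.
2. **Synopsis, Design and Statistical Methodology rows:** state that the effectiveness conclusion concerns active versus sham stimulation with this montage, and that site specificity of the targeting method is not tested.

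No new arm, outcome or data collection is needed. The Design row is already written in the past tense, so an added arm may no longer be possible. The wording change works whether or not the trial is still blinded. The cost is a narrower claim about the targeting method; a test of site specificity would be left to a later trial with an active control site and a justified sample size.
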